⁷ Includes assessments of ocular pain and irritation. See Section 8.0 of protocol for information on how to record AEs and how to determine attributionality (relatedness) of AE to study procedures (including cataract surgery) or study drug.

⁸ Ocular inflammation assessment using ACC count, anterior chamber flare grade, bulbar conjunctival injection, sclera - ciliary flush and corneal edema.

⁹ IOP should (but not required) be assessed at each visit within ± 2 h of the IOP assessment time at Visit 1.

¹⁰ Only performed in the subjects in the Endothelial Cell Sub-study at participating centers. The parameters are: endothelial cell density (cells/mm²), percent hexagonality and coefficient of variation. Performed in both eyes at the Screening visit and in the study eye at Visit 6 (POD22) and Visit 7 (POD85).

¹¹ The first dose of study drug should be instilled into the study eye at the clinic visit under supervision of clinic staff. The second dose on POD1 can be administered at home. Subjects who are rescued will not continue to instill study drug or receive further diary cards but will remain in the study to complete the procedures/assessments through Visit 6 (POD22) (Main Study) or Visit 7 (Endothelial Cell Sub-study).

¹² The site must contact the subject via the subject's preferred method on POD14 to remind him/her not to instill study drug on POD15 and to bring the bottle of study drug and the dosing diary back to the site at the POD15 visit. In addition, the subjects in the Endothelial Cell Sub-study will be sent US mail/email/voicemail/text message reminders on ~POD50 and ~POD78 to return for Visit 7 (POD85).

¹³ Concomitant medications used for rescue should be reported in the eCRF.

[figure not shown]
¹⁴ AEs and Concomitant Medications should only be recorded on Day 0 if they result in disqualification (i.e., screen failure) of the subject; otherwise, the AEs and Concomitant Medications applicable to Day 0 should be recorded when the subject returns for Visit 2 (POD1).

¹⁵ Any AEs reported to the site during the POD14 contact or as a result of the POD50/POD78 reminders must be recorded in the source documents. Further assessment of any reported AEs may require an Unscheduled Visit if medically significant or they may be assessed, as appropriate, during Visit 5 (POD15) or Visit 7 (POD85), respectively.

1.0 INTRODUCTION

1.1 OVERVIEW

APP13007 is an ophthalmic nanosuspension that is prepared by dispersing [REDACTED]
[REDACTED], a corticosteroid, with a mixture of excipients in a multi-dose preserved aqueous

1.2 BACKGROUND

1.2.1 [REDACTED]

Corticosteroids regulate cellular signaling, immune function, inflammation and protein synthesis, and like other corticosteroids, CP has anti-inflammatory and vasoconstrictive properties. The mechanism of the anti-inflammatory activity of CP is unclear, but it is thought to act by inducing lipocortins, proteins that inhibit phospholipase A2, an enzyme that releases arachidonic acid from membrane phospholipids. By inhibiting phospholipase A2, lipocortins control the biosynthesis of potent mediators of inflammation such as prostaglandins and leukotrienes.

CP is an analog of prednisolone with a very high degree of activity at the glucocorticoid receptor and only slight degree of mineralocorticoid activity ([Clobex® 2018](#)). It is reported to be the most potent corticosteroid in terms of binding affinity to the glucocorticoid receptor and resulting pharmacological effects ([Olsen 1986](#)), ([Jacob 2006](#)). CP has been used in dermal applications including ointments, creams and shampoos, where its efficacy and safety has been well-established ([Clobex® 2018](#)); ([Temovate® 2000](#)); ([Olsen 1986](#)); ([Hengge 2006](#)); ([Feldman 2009](#)).

1.2.2 Pain and Inflammation Following Cataract Surgery

Despite modern advances in surgical technique, trauma that occurs during cataract removal and intraocular lens placement regularly leads to some degree of inflammation. The cellular damage on the surface of the cornea activates an inflammatory process that manifests initially as hyperemia, corneal edema, and increased anterior chamber cells and flare. More serious complications such as corneal edema, increases in intraocular pressure (IOP), cystoid macular edema, and posterior capsule opacification may result if the inflammatory process is not managed appropriately ([Tennant 1978](#)) ([Apple 1992](#)). For this purpose, a post-cataract surgery regimen of anti-inflammatory agents (such as corticosteroids) is typically prescribed because it reverses inflammation, pain and discomfort and reduces the risk of further complications. When administered at the time of surgery and during the immediate postoperative period,

corticosteroids can reverse the clinical and non-clinical manifestations of inflammation ([Leopold 1985](#)) ([Aptel 2017](#)).

1.2.3 Rationale for Development of APP13007

Topical ocular administration of corticosteroids is a well-established therapy for the treatment of inflammation and pain after ocular surgery ([Aptel 2017](#)), and several marketed products are currently available that contain active ingredients such as dexamethasone, prednisolone, loteprednol etabonate and difluprednate.

[figure not shown]
CP has been used for over 30 years in the US, Europe and Japan to treat the inflammatory and pruritic manifestations of corticosteroid responsive dermatoses such as psoriasis, eczema and atopic dermatitis. CP has not been previously developed for ophthalmic use, presumably due to its lack of aqueous solubility. Nevertheless, given its increased potency, an aqueous ophthalmic formulation of CP has the potential to produce rapid clearance of anterior chamber cells (ACC), return of visual acuity and relief of pain after ocular surgery, surpassing the effectiveness of corticosteroids currently on the market.

APP13007 is an ophthalmic nanosuspension that is prepared by dispersing nanomilled CP with a mixture of excipients. The proprietary nanomilling technology allows CP to be formulated as an aqueous suspension. This suspension of CP nanoparticles in APP13007 is designed to promote efficient penetration of CP into the eye upon ocular surface instillation, thus delivering therapeutically relevant concentrations of CP to the target tissues within the eye.

1.3 NONCLINICAL STUDIES

Multiple nonclinical pharmacology, pharmacokinetics, and toxicology studies have been conducted with various formulations of APP13007, and these are summarized in the APP13007 Investigator Brochure.

1.3.1 Primary Pharmacology

1.3.2 Pharmacokinetics

1.3.3 Toxicology

[REDACTED] The toxicology studies suggest that potential systemic effects in human subjects with ocular instillations of APP13007 are those typical of corticosteroids in general and that have been seen with approved dermal CP products, such as Temovate® and Clobex® ([Temovate® 2000](#)); ([Clobex® 2018](#)).

The data from repeat dose toxicology studies did not identify any unacceptable risk for human subjects.

1.4 HUMAN STUDIES

Two clinical studies have been completed with APP13007, and details of the subject populations, study dosing, conduct and results are summarized in the APP13007 Investigator Brochure.

1.4.1 CPN-201: A Phase 2 Safety and Preliminary Efficacy Study Post Cataract Surgery

[figure not shown]
This was a multi-center, randomized, double-masked, placebo-controlled, parallel-group Phase 2 study conducted in two parts (Parts A and B) to evaluate two APP13007 dose strengths and two dosing frequencies in subjects who had undergone routine cataract surgery and lens implantation. On Post-Operative Day 1 (POD1), subjects who met eligibility criteria were enrolled in the study

and randomized to one of the study treatments instilled in the operated study eye: Treatment 1 or 2 in Part A (1:1 ratio); Treatment 3, 4, 5, or 6 in Part B (1:1:1:1 ratio). A total of 45 subjects were randomized in Part A and 87 subjects randomized in Part B.

- Treatment 1: 1 drop 0.05% APP13007 BID for 21 days
- Treatment 2: 1 drop 0.05% matching vehicle placebo BID for 21 days
- Treatment 3: 1 drop 0.05% APP13007 BID for 3 days followed by 1 drop 0.05% APP13007 QD for 11 days
- Treatment 4: 1 drop 0.05% matching vehicle placebo BID for 3 days followed by 1 drop 0.05% matching vehicle placebo QD for 11 days
- Treatment 5: 1 drop 0.1% APP13007 BID for 3 days followed by 1 drop 0.1% APP13007 QD for 11 days
- Treatment 6: 1 drop 0.1% matching vehicle placebo BID for 3 days followed by 1 drop 0.1% matching vehicle placebo QD for 11 days

1.4.1.1 Safety Results

The 0.05% APP13007 and 0.1% APP13007 dosing regimens were well-tolerated with a safety profile similar to the matching placebo vehicles.

1.4.1.2 Efficacy Results

[REDACTED]

1.4.1.3 Conclusion

The safety and efficacy results from study CPN-201 support the further clinical evaluation of 0.05% APP13007 BID for the treatment of inflammation and pain following ocular surgery.

1.4.2 CPN-102: A Phase 1 Pharmacokinetic Study in Healthy Subjects

CPN-102 was an open-label, sequential dosing, Phase 1 pharmacokinetic (PK) study to evaluate the systemic exposure of CP following ocular instillation of 0.05% APP13007 in healthy subjects. [REDACTED]

[REDACTED]

[REDACTED]

[REDACTED]

[REDACTED]

[REDACTED]

[REDACTED]

1.4.2.1 Safety Results

The 0.05% APP13007 drops were well-tolerated. There were no AEs related to the study drug.

1.4.2.2 Pharmacokinetic Results

[REDACTED]

1.4.2.3 Conclusion

[REDACTED]

1.4.3 CPN-301: A Multicenter, Randomized, Double-Masked, Placebo-Controlled, Parallel-Group Study to Evaluate the Efficacy and Safety of APP13007 for the Treatment of Inflammation and Pain after Cataract Surgery

This Phase 3 study will evaluate APP13007 0.05% in comparison to the matching vehicle placebo in a randomized, parallel-group, double-masked fashion. The design of this study is identical to that of the Main Study in the current protocol.

1.5 RISK/BENEFIT ASSESSMENT

1.5.1 Potential Risks

1.5.1.1 Potential Risks Anticipated Based on Results from the GLP Rabbit Toxicology Studies with APP13007

[REDACTED]

1.5.1.2 Potential Risks Anticipated Based on Results from the Human Studies with APP13007

As summarized in the APP13007 Investigator Brochure and in [Section 1.4.1.2](#) and [Section 1.4.2.2](#), 0.05% APP13007 BID for 21 days was well-tolerated. [REDACTED]

[REDACTED]

[REDACTED]

[REDACTED]

[REDACTED]

[REDACTED]

[REDACTED]

[REDACTED]

[REDACTED]

the systemic tolerability profile after ocular instillation of 0.05% APP13007 BID for 14 days is expected to be considerably better than that for dermal CP products summarized below.

1.5.1.3 Potential Risks Associated with the Use of CP in the Treatment of Corticosteroid-Responsive Dermatoses

There is extensive experience with CP in the treatment of inflammatory and pruritic manifestations of corticosteroid-responsive dermatoses, where its safety and anti-inflammatory profile has been well defined ([Olsen 1986](#)); ([Hengge 2006](#)); ([Feldman 2009](#)). These risks are summarized in the APP13007 Investigator's Brochure.

Potential non-ocular risks include:

- Hypothalamic-Pituitary-Adrenal (HPA) Axis Suppression. Recovery of HPA axis function is generally prompt upon discontinuation of topical corticosteroids.
- Cushing's syndrome, hyperglycemia, and unmasking of latent diabetes mellitus. Use of more than one corticosteroid-containing product at the same time may increase the total systemic corticosteroid exposure.
- Skin: Allergic contact dermatitis may occur.
- Pregnancy and Nursing (Breast-feeding) Mothers:
 - Corticosteroids are teratogenic in laboratory animals when administered systemically at relatively low dosage levels (Pregnancy Category C). When administered subcutaneously, CP was a significant teratogen in both the rabbit and mouse. Females of child-bearing potential are eligible to participate in this

study only if they have a negative urine pregnancy test on POD1 pre-randomization and they agree to use highly effective contraception or abstain from sexual activity from POD1 to POD22. Note: Pregnant and/or nursing (breast-feeding) mothers are excluded from participation in this study.

- Systemically administered corticosteroids appear in human milk and could suppress growth, interfere with endogenous corticosteroid production, or cause other untoward effects. It is not known whether ocular administration of APP13007 could result in sufficient systemic absorption of CP to produce detectable concentrations in human milk.

Potential ocular risks are summarized below.

1.5.1.4 Potential Class-Related Ocular Risks Associated with Corticosteroid Therapies for the Treatment of Ocular Inflammation and Pain after Ocular Surgery

The active ingredient in APP13007, ■■■, is a potent corticosteroid so it has the following anticipated ocular risks associated with the corticosteroid class:

- Intraocular pressure (IOP) increase – prolonged use may result in glaucoma with damage to the optic nerve, defects in visual acuity and field of vision.
- Cataracts – Prolonged use ■■■ may result in posterior subcapsular cataract formation in the non-operated eye.
- Delayed healing – Use ■■■ after cataract surgery may delay healing and increase the incidence of bleb formation. In those diseases causing thinning of the cornea or sclera, perforations have been known to occur with the use of topical corticosteroids.
- Risk of Infection
 - Bacterial infections – Prolonged use ■■■ may suppress the host immune response and thus increase the hazard of secondary ocular infections. In acute purulent conditions, corticosteroids may mask infection or enhance existing infection.
 - Viral infections – Use of ocular corticosteroids may prolong the course and may exacerbate the severity of many viral infections of the eye (including herpes simplex).
 - Fungal Infections – Fungal infections of the cornea are particularly prone to develop coincidentally with long-term local corticosteroid application. Fungus invasion must be considered in any persistent corneal ulceration while a subject is participating in this clinical trial.

In clinical studies evaluating the use of corticosteroids after ocular surgery, ocular adverse reactions that occurred in 5% to 15% of subjects included corneal edema, ciliary and conjunctival hyperemia, eye pain, photophobia, posterior capsule opacification, anterior chamber cells, anterior chamber flare, conjunctival edema, and blepharitis. Other ocular adverse reactions occurring in 1% to 5% of subjects included reduced visual acuity, punctate keratitis, eye inflammation, and iritis. Ocular adverse reactions occurring in less than 1% of subjects included application site discomfort or irritation, corneal pigmentation and striae, episcleritis, eye pruritus, eyelid irritation and crusting, foreign body sensation, increased lacrimation, macular edema, sclera hyperemia, and uveitis. Most of these reactions may have been the consequence of the surgical procedure.

1.5.1.5 Potential Risks Associated with the APP13007 Formulation

[REDACTED]

1.5.2 Risk Mitigation Plan

Given the potential risks noted above, a risk mitigation plan will be used to mitigate risks for subjects enrolled into the study. The Risk Mitigation Plan is shown in Table 2.

1.5.3 Contraindications

[REDACTED]

APP13007, as with other corticosteroids, is contraindicated in the presence of active viral diseases of the cornea and conjunctiva including epithelial herpes simplex keratitis (dendritic

keratitis), vaccinia, and varicella, and also in subjects with mycobacterial infection of the eye and fungal diseases of ocular structures.

APP13007 must not be administered (i) to women of child-bearing potential without a negative urine pregnancy test on POD1 prior to randomization and agreement to use highly effective contraception or abstain from sexual activity from POD1 to POD22 or (ii) to pregnant or nursing (breast-feeding) woman.

1.5.4 Potential Benefits

Topical ocular administration of corticosteroids is a well-established therapy for the treatment of inflammation and pain after ocular surgery, with multiple marketed products currently available that utilize corticosteroids as the active ingredient such as dexamethasone (Maxidex®), prednisolone (PredForte®), loteprednol etabonate (Lotemax®, Inveltys®, Lotemax SM®), and difluprednate (Durezol®). In all clinical trials, corticosteroid therapies were dosed at a frequency of twice daily or more frequently.

As summarized in the APP13007 Investigator's Brochure, in Study CPN-201 a greater proportion of subjects treated with APP13007 0.05% BID had complete clearing of anterior chamber cells and complete resolution of ocular pain compared to placebo-treated subjects. Thus, it is likely that subjects randomized to active APP13007 will experience a clinically-meaningful reduction in inflammation and pain following cataract surgery.

It is known from large clinical trials of products for the treatment of inflammation and pain after ocular surgery that a proportion of subjects randomized to placebo improve in the days following surgery (Lotemax® Product Insert 2018; Durezol® Product Insert 2017). Thus, there may be a marginal benefit observed in some of the subjects enrolled into the study who are randomized to the matching vehicle placebo.

1.5.5 Assessment of Potential Risks and Benefits

This is a placebo-controlled study in which subjects will be randomized 1:1 to APP13007 or matching vehicle placebo. Subjects randomized to active APP13007 may benefit from the treatment by reduction in inflammation and pain, while the risks associated with active APP13007 treatment are likely to be low and manageable. This assessment is supported by the results of the nonclinical (See [Section 1.3](#)) and clinical studies (See [Section 1.4](#)) that are summarized in detail in the APP13007 Investigator's Brochure.

Subjects randomized to placebo are not expected to benefit from the study treatment, but a proportion of subjects receiving placebo may show improvement of inflammation in the days following surgery. Furthermore, the risks to subjects randomized to placebo in this study are mitigated as much as possible. Specifically, the protocol contains instructions for careful

monitoring of safety and efficacy endpoints during the trial to identify subjects who show minimal improvement or worsening of the clinical conditions so that appropriate mitigation steps can be taken, including, but not limited to, withdrawal from study treatment and commencement of appropriate rescue medication.

[figure not shown]
[figure not shown]
Overall, the risk:benefit analysis supports the evaluation of 0.05% APP13007 and matching vehicle placebo administered BID for 14 days after cataract surgery.

Table 2: Risk Mitigation Plan

Potential Risk	Management	Comments
Risk Associated with Lack of Efficacy		
Minimal reduction or worsening of inflammation and pain endpoints or other factors suggesting lack of efficacy	Inflammation and pain endpoints will be monitored during the study. Guidance criteria and procedures for the rescue of subjects are provided in Section 9.4 of this protocol.	Minimal reduction or worsening of inflammation and pain endpoints or other factors suggesting lack of efficacy
Risk Associated with Unexpected Safety Events		
Unexpected safety events	Safety endpoints will be monitored during the trial. The Investigator will discuss unexpected safety events with the Study Medical Monitor who will then discuss unexpected safety events with the Sponsor to determine whether study drug should be stopped and rescue procedures commenced.	The toxicology studies with APP13007 indicate that there is a low risk of ocular toxicity. The risks of systemic exposure to CP following dermal application are well characterized. [REDACTED] [REDACTED] [REDACTED] [REDACTED] Nevertheless, the Investigator should be alert to the possibility that unexpected safety events may occur. The list of expected safety events is including in Section 1.5.1 and in the APP13007 Investigator's Brochure.

Potential Risk	Management	Comments
Risks Associated with the Corticosteroid Class		
Intraocular pressure (IOP) increase	
IOP will be monitored during the study.
 
The protocol excludes subjects who may be at increased risk of steroid-induced IOP increase, e.g. subjects with a history of raised IOP/glaucoma and subjects with IOP >30 mmHg at the POD1 pre-randomization assessment.
 
Section 9.5 includes stopping criteria for study drug due to IOP increase and criteria for initiation of IOP-lowering medication.
 
After Randomization, the management of IOP > 30 mmHg or IOP ≥ 21 mmHg AND an IOP increase > 10 mmHg from pre-dose baseline is described in Section 9.5.2.
	
There was no clinically-meaningful APP13007-related elevation of IOP in the toxicology studies and in Study CPN-201.
 
Prolonged use of CP may result in glaucoma with damage to the optic nerve, defects in visual acuity and fields of vision.
 
An IOP ≥ 30 mmHg after randomization should be reported as an AE.

Cataracts	
The lens structure and posterior capsular opacification (POC) in the study eye will be monitored at each clinic visit throughout the study.
 
The lens in the non-operated eye will be evaluated at Screening, Visit 6 (POD22) and Early Termination/Withdrawal visits.
	
Delayed Healing	
Subjects with thinning of the cornea or sclera are excluded because of the greater risk of perforations with the use of topical steroids.
 
Protocol includes stopping criteria for study drug if the Investigator, in consultation with the Study Medical Monitor, is concerned about delayed healing.
	
Use of APP13007 may delay healing after cataract surgery and increase the incidence of bleb formation. There were no reports of delayed healing after cataract surgery in Study CPN-201.

Potential Risk	Management	Comments
Risk of Infection	
Subjects with on-going ocular bacterial, viral or fungal infections are excluded from the study.
 
Ocular infections occurring during the study should be assessed and treated appropriately.
 
The Investigator should discuss with the Study Medical Monitor whether to stop study drug if ocular infection occurs.
	
Use of APP13007 may suppress the host immune response and increase the hazard of ocular infections. This risk is likely to be low based on data from studies of other steroids products approved for the treatment of inflammation and pain after ocular surgery.

Hypothalamic-Pituitary-Adrenal Axis (HPA) Suppression	
Monitor for symptoms and signs of reduced adrenal function (including fatigue, muscle weakness, loss of appetite and weight, abdominal pain, nausea and diarrhea, low blood pressure, depression and irritability, salt craving and hypoglycemia).
 
The Investigator should discuss with the Study Medical Monitor who will then discuss with the Sponsor whether to stop study drug.
	
While systemic absorption of topical corticosteroids can produce reversible HPA axis suppression with the potential for glucocorticoid insufficiency after withdrawal from treatment, this risk is likely to be very low
 
[REDACTED]
 
[REDACTED]
 
[REDACTED]
 
[REDACTED]
 
[REDACTED]
 
Nevertheless, Investigators should be aware that the symptoms and signs of reduced adrenal function can be nonspecific and they should remain alert to the possibility that this may occur.

Effects related to excessive corticosteroid pharmacology	
Monitor for symptoms and signs of excess corticosteroid pharmacology such as Cushing's syndrome, hyperglycemia, and unmasking of latent diabetes mellitus.
 
The Investigator should discuss with the Study Medical Monitor who will then discuss with the Sponsor whether to stop study drug.
	
These effects have been reported after dermal use of CP and result from systemic absorption of topical CP.
 
[REDACTED]
 
[REDACTED]
 
[REDACTED]
 
[REDACTED]

Potential Risk	Management	Comments
Pregnancy Category C/Fetal effects	
Women of child-bearing potential are excluded from the study if they have a positive urine pregnancy test on POD1 pre-randomization and/or do not agree to use highly effective contraception or abstain from sexual activity.
 
Pregnant and/or nursing (breast-feeding) mothers are excluded from the study.
	
Corticosteroids are known teratogens in laboratory animals when administered systemically at relatively low dosage levels.
 
Skin Irritation	
If irritation develops appropriate therapy should be instituted.
 
The Investigator should notify the Study Medical Monitor in advance if study drug is going to be stopped.
	
Allergic contact dermatitis may occur with CP.
 
Other skin reactions have been described with topical dermal products (See APP13007 Investigator's Brochure).

Other Potential Risks 		

Potential Risk	Management	Comments
Hypersensitivity Reactions	
Subjects are excluded from the study if they have a history of hypersensitivity to CP, corticosteroids, [REDACTED] [REDACTED] [REDACTED] [REDACTED] [REDACTED]
 
If hypersensitivity reaction occurs, the Investigator should discuss with the Study Medical Monitor who will then discuss with the Sponsor Medical Monitor whether to stop study drug.
	
Adverse reactions reported in clinical studies evaluating the use of corticosteroids after ocular surgery.	Most of these adverse reactions may have been the consequence of the surgical procedure and should be managed according to standard-of-care procedures.	Ocular adverse reactions reported in completed clinical studies of APP13007 are summarized in Section 1.5.1 .

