- *Visit 1 (Screening):* Measurement of corneal endothelial cell parameters (endothelial cell density [cells/mm²], percent hexagonality and coefficient of variation) in both the planned study eye and non-study eye. Collect information on contact lens use.
- *Visit 6 (POD22)/Early Termination:* Measurement of corneal endothelial cell parameters in the study eye.
- Subjects will be contacted twice (on ~ POD50 and ~ POD78) by USPS mail, email, voicemail or phone text after Visit 6 to remind them that they need to return for Visit 7.

- *Visit 7:* POD85 (\pm 4 days). Subjects who had the measurement of corneal endothelial cell parameters at Visit 1 (Screening) will return for a final measurement of corneal endothelial cell parameters in the study eye and assessment of adverse events and concomitant medications (approximately three months after starting the study drug). Final Visit for the Endothelial Cell Sub-study.

A detailed summary of study events is provided in Table 1 (Schedule of Events) and a study design schematic is provided in Figure 1 (Study Schematic).

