7.3.1 List of Safety Assessments

- AEs
- ETDRS Assessment of Best Corrected Visual Acuity by Pinhole Method
- Slit Lamp Biomicroscopy assessment of the following signs of inflammation: corneal edema, ciliary flush, bulbar conjunctival injection. The assessments in the non-study eye will include an assessment of the lens
- IOP Measurement using Goldmann applanation tonometry
- Dilated Ophthalmoscopy assessment of the vitreous, retina, macula, choroid, and optic nerve with cup/disc ratio, and an assessment of the presence and severity of a cataract if present in the non-study eye
- Corneal Endothelial Cell Parameters: corneal endothelial cell density (cells/mm²), percent hexagonality and coefficient of variation (only in Endothelial Cell Sub-study)

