7.3.1.3 Slit Lamp Biomicroscopy

In addition to the assessment of ACC and ACF ([Section 7.2.2.1](#)), the following safety parameters will be evaluated at Visits 1 through 6 as indicated in Table 1 using the following scales during the slit lamp examination:

Bulbar Conjunctival Injection

Grade	Description
0	Absent
1	Mild
2	Moderate
3	Severe

Sclera - Ciliary Flush

Grade	Description
0	Absent
1	Mild
2	Moderate
3	Severe

Corneal Edema

Grade	Description
0	Absent
1	Mild
2	Moderate
3	Severe

The lens in the non-study eye will be classified as phakic, pseudo-phakic or non-phakic.

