7.3.3 Dilated Ophthalmoscopy

A dilated fundus examination will be performed according to the Investigator's standard technique at the Visits indicated in Table 1. The Investigator should evaluate the vitreous, retina, macula, choroid, and optic nerve with cup/disc ratio and will note normal/abnormal findings. If a cataract is present in the non-study eye, the Investigator will make an assessment of its location and severity as described below.

The Investigator will determine whether or not abnormalities observed at Visit 1 (Screening) would exclude a subject from study participation.

If a subject had an abnormality in the study eye or non-study eye at Visit 1 (Screening), the Investigator should make an assessment whether there has been a change at Visit 6 (POD22) or at Early Termination/Withdrawal and record this in the source document and eCRF. It is recommended that the Investigator refer to the documentation at Visit 1 (Screening) when making the assessment of a change in status.

Grading a Cataract in the Non-Study Eye

For subjects with phakic lens in the non-study eye, when present, a cataract will be assessed (a) by location - Nuclear, Cortical, and Posterior Subcapsular, and (b) by severity (minimal, mild, moderate or severe). [Appendix B](#) provides a guidance that may be used to grade the severity of a nuclear, cortical or posterior subcapsular cataract in the non-study eye.

If a subject had a cataract in the non-study eye at Visit 1 (Screening), the Investigator should make an assessment whether there has been a change in the size or composition of the cataract at Visit 6 (POD22) or at Early Termination/Withdrawal and record this in the source document and eCRF. It is recommended that (i) the cataract grading is performed by the same Investigator at Screening and Visit 6 (POD22) or at Early Termination/Withdrawal, and (ii) the Investigator refers to the documentation of the non-study eye at Visit 1 (Screening) when making the assessment of change in the lens status.

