11.3.3 Slit Lamp Biomicroscopy

Slit Lamp biomicroscopy assessments will evaluate corneal edema, ciliary flush, bulbar conjunctival injection. The assessments for the study eye will be performed from Screening through EOMS. The assessments for the non-study eye will be performed at Screening and EOMS. The following grades will be used for the assessments.

Grade	Description
0	Absent
1	Mild
2	Moderate
3	Severe

The number and percentage of subjects in each grade category of the assessments will be tabulated by treatment group at each post-surgery scheduled visit through EOMS for the study eye.

A shift table of assessment grades from Screening to EOMS for both eyes will be presented by treatment group.

In addition, the non-study eye lens status (phakic, non-phakic or pseudophakic) will be assessed at Screening. The number and percentage of subjects in each status category will be tabulated.

The data of the biomicroscopy assessments for safety evaluation will be presented in a data listing.

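### Table 2 promises study-eye lens and posterior-capsule monitoring at each clinic visit, but no procedure, schedule item or SAP table provides for it, so these findings are not systematically captured

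*Protocol*

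**What the plan says.** Protocol Section 1.5.2 refers to Table 2 for the risk mitigation plan. The Cataracts row, among the corticosteroid-class risks, makes two separate commitments:

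- Study eye: "The lens structure and posterior capsular opacification (POC) in the study eye will be monitored at each clinic visit throughout the study".
- Other eye: "The lens in the non-operated eye will be evaluated at Screening, Visit 6 (POD22) and Early Termination/Withdrawal visits".

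The sections that tell sites what to do read as follows:

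- Table 1, footnote 8, defines the slit-lamp examination: "Ocular inflammation assessment using ACC count, anterior chamber flare grade, bulbar conjunctival injection, sclera - ciliary flush and corneal edema".
- Section 7.3.1, on slit lamp, adds a lens item for one eye: "The assessments in the non-study eye will include an assessment of the lens".
- Section 7.3.1.3 gives scales for conjunctival injection, ciliary flush and corneal edema, then: "The lens in the non-study eye will be classified as phakic, pseudo-phakic or non-phakic".
- Section 7.3.3, on dilated ophthalmoscopy: "The Investigator should evaluate the vitreous, retina, macula, choroid, and optic nerve with cup/disc ratio and will note normal/abnormal findings". Cataract location and severity are then graded in the non-study eye. Table 1 schedules this examination at Screening and Visit 6.
- Section 3.2.1 says that Sub-study subjects at Visit 7 "will return for a final measurement of corneal endothelial cell parameters in the study eye and assessment of adverse events and concomitant medications". Table 1 has no slit-lamp entry for that visit.

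In the SAP, Section 11.3.3 states: "Slit Lamp biomicroscopy assessments will evaluate corneal edema, ciliary flush, bulbar conjunctival injection". It also tabulates the non-study eye's lens status at Screening. Section 11.3.4 provides a cataract shift table for the non-study eye.

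**The concern.** A named mitigation has no procedure behind it. A site that carries out Section 7 as written has no instruction to look at, grade or record the intraocular lens or posterior capsule of the operated eye. The SAP has no place to report such a finding apart from the adverse-event tables.

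Posterior capsular opacification matters to this trial on the protocol's own account. Section 1.2.2 lists it among the complications of poorly managed inflammation after cataract surgery, and Section 1.5.1.4 lists it among reactions seen in post-surgical corticosteroid studies. It could therefore arise in either arm, so a comparison between arms is of interest. Without a structured item, that comparison rests on what investigators choose to report. A low count could mean that the finding was rare or that it was seldom looked for.

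**Working it through.** No arithmetic decides this point. The check was to compare the Table 2 commitment with every place where a study-eye lens or capsule assessment could appear.

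| Place | Study eye: lens or capsule | Non-study eye: lens |
|---|---|---|
| Protocol Table 2, Cataracts row | Yes, each clinic visit | Yes: Screening, Visit 6, Early Termination |
| Protocol Table 3, endpoints | None named | None named |
| Protocol Table 1, footnote 8 | None (five inflammation signs) | None |
| Protocol 7.3.1, slit lamp | None | Lens assessment |
| Protocol 7.3.1.3 | None (three graded signs) | Phakic status |
| Protocol 7.3.3 and Appendix B | None | Cataract location and severity |
| SAP 11.3.3 | None (three signs tabulated) | Lens status at Screening |
| SAP 11.3.4 | None | Cataract shift, Screening to end of Main Study |

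The second commitment in the row is carried through: the non-study eye has an assessment, a grading guide and a shift table. The first appears only in Table 2. Because the row treats the two eyes in separate sentences, the study-eye sentence does not look like a slip for the other eye.

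**Visits affected.** Table 1 gives the study eye five post-surgery slit-lamp examinations (Visits 2, 3, 4, 5 and 6). None has a lens or capsule item. Visit 7 has no slit-lamp examination. It applies to about 176 of about 370 randomized subjects: 176 / 370 = 0.476, or about 48%. For them the each-visit wording could not be met at Visit 7 even if an item were added to every existing slit-lamp examination.

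**What remains.** Section 7.3.1.1 counts events revealed by examination as AEs and requires clinically relevant deterioration in a clinical finding to be recorded. SAP 11.2 tabulates study-eye ocular TEAEs by preferred term and arm through the end of the Main Study, and summarizes later Sub-study AEs separately. This route gives subjects with a reported event. It does not give the number of eyes in which the capsule was examined, or presence and absence by visit.

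**The case against.** The strongest reply is that monitoring need not mean a dedicated field and table. Other rows of Table 2 ask for monitoring of symptoms and signs of adrenal suppression or corticosteroid excess, and those rows rely on clinical observation and AE reporting. Investigators use the slit lamp at Visits 1 to 6 in any case. Study-eye acuity is measured at each of those visits, and SAP 11.3.2 tabulates worsening of two lines or more. A capsule finding of clinical relevance must be reported as an AE.

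Much of this stands, and it sets the limits of the point:

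- A reader might infer that these findings are not captured at all, or that an absence of cases could only reflect non-collection. The AE provisions in Section 7.3.1.1 and SAP 11.2 do not support that.
- A reader might also infer that Section 7.3.1.1 keeps such findings out of the eCRF. Its restriction concerns complaints expected after surgery. Opacification is an examination sign, and that section sends even a complaint to the eCRF when it comes with an adverse slit-lamp finding.
- It is tempting to apply the 5% to 15% in Section 1.5.1.4 to the arm sizes. That band is shared by a list of reactions in other trials, with no follow-up length and no rate specific to opacification. The protocol adds that most of these reactions may have come from the surgery. It cannot serve as a forecast here.
- The cataract risk described in Section 1.5.1.4 lies in the non-operated eye, and that risk is both assessed and analyzed.

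The reply does not remove the mismatch. The Cataracts row names a structure, an eye and a frequency, unlike the general wording of the other rows. Acuity is not specific to the capsule, and AE reporting depends on the capsule being examined, which Section 7 does not require.

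**Conclusion.** The inconsistency holds. Table 2 commits to study-eye lens and posterior-capsule monitoring at each clinic visit, while the schedule, Section 7 and the SAP contain no matching item, and Visit 7 has no slit-lamp examination. The findings are therefore not systematically captured. Clinically relevant ones can reach the AE tables, but without a denominator of eyes examined and without a by-visit comparison between arms.

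The weight is that of a safety-data gap that should be closed. It does not touch the primary endpoints, sample size or error control, and the documents give no basis for estimating how many findings would be missed.

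The conclusion rests on the protocol and SAP alone. The eCRF and Study Reference Manual were not available, and either may contain a field. If one does, the protocol procedures and SAP would still need to be aligned with it.

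**What to change.** Reconcile Table 2 with Section 7.3, Table 1 footnote 8 and SAP 11.3.3:

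1. In Section 7.3.1.3 and footnote 8, add a simple study-eye item to the existing slit-lamp examination at Visits 2 to 6 and at Early Termination where the Visit 6 assessments are done. Record the intraocular lens as normal or abnormal, and posterior capsular opacification as absent or present. A severity grade is not needed; the scale used for the other signs was not defined for the capsule.
2. In SAP 11.3.3, tabulate both items for the study eye by arm and visit, with the number of eyes examined as the denominator.
3. In Table 2, limit the study-eye sentence to the visits that have this examination, so that Visit 7 is not claimed.

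The cost is two eCRF fields, one table and a small amendment. No visit or procedure is added, because the slit-lamp examination already takes place at the visits concerned. Extending the item to Visit 7 would need a new examination there and is not proposed.
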